The most recent evidence obtained from trials and studies has documented the consumption of breakfast and its associated health benefits. (Betts, Richardson et al. 2014). Several studies have also investigated the relationship between eating at night and cardiovascular and metabolic disorders, including obesity. (Madzima, Panton et al. 2014).

The importance of the circadian rhythm in the regulation of food intake as human behavior and metabolism has already been described. However, little is known about how energy intake is distributed in the day in existing populations, and its potential association with obesity. (Almoosawi, Vingeliene et al. 2016).

In general, there is no real scientific evidence to support whether a 6-course or one-only three-course meal plan is more beneficial for your health. Therefore, there is no evidence to show the relationship between meal times and glycemic variability in patients with type 2 diabetes mellitus who are overweight or obese.

On the other hand, glycemic variability (VG) is defined as the oscillations in glucose concentration throughout the day, including hypoglycemia and glucose elevation in the postprandial period. It has been proposed that VG is a determinant of the microvascular complications of diabetes mellitus, regardless of hyperglycemia. (Brownlee and Hirsch 2006).

However, recent studies emphasize glycosylated hemoglobin (HbA1c) as a risk determinant for diabetes complications, but no mention is made of how glucose fluctuations influence. (Ceriello and Ihnat 2010).

In a study conducted at Kyoto University Hospital about blood glucose variability if it was associated with quality of life and treatment satisfaction in patients with type 1 diabetes, they mention something very important, neither glucose variability nor hypoglycemia is precisely detected by HbA1c. (Ayano-Takahara, Ikeda et al. 2015).

It has been shown in several studies that the complications associated with diabetes mellitus are largely due to fluctuations in glucose concentration throughout the day. For example in a study that was done with animals where they confirmed that glucose oscillations, increases the risk particularly for all the pathogenesis that is involved in the complications of diabetes. And in studies with humans it was confirmed that glucose fluctuations produces an increase in free radical levels and an increase in endothelial dysfunction. (Cavalot 2013).

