### f) Duration of individual follow-up

12 weeks			
14. Temporality of the study.			
Type of study		Select an option	
Retrospective			
Prospective		X	
15. Process of assigning the groups under study			
Maniobra	Yes (Include the corresponding information)	No	does not apply
Randomization	X		
Open study			
Simple blind study	X		
Double blind study			
Triple blind study			
16. Descripción de las maniobras o las intervenciones			
50 patients with DM2 will be recruited from the Institute's Diabetes clinic who are overweight or obese and who are between 40 and 70 years old and who are with oral hypoglycemic agents, with an HbA1c less than 9% and who are less than 10 years old of evolution			
Clinical evaluation			
A complete medical history and physical examination will be performed in order to confirm the presence of the inclusion criteria and rule out the presence of exclusion criteria. An anthropometric evaluation and body composition (waist and hip circumference, height, weight and percentage of fat) will be made, as well as blood pressure measurement. An interrogation will be conducted to document a history of coronary heart disease, menopausal status and use of hormonal therapy, smoking, alcohol consumption and physical activity (through a validated physical activity questionnaire in the Mexican population).			
Nutritional assessment.			
Will be performed			
Patients will be divided into 2 groups without distinction.			
. The first group that will be 25 patients will undergo a hypocaloric regimen with caloric restriction of 15% of their usual daily consumption with a distribution of macronutrients of 40% in Carbohydrates, 20% of Protein and 40% of Lipids in three times of food (TC6) during a period of 12 weeks in which the following variables will be measured (Weight, Glycemic Variability: Monitor, HbA1c, Glycemas, Lipid Profile, Oxidative, FGF-21, Blood Pressure and Hunger-Satiety levels.)			

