The second group that will be 25 patients will undergo a hypocaloric regimen with caloric restriction of 15% of their usual daily consumption with a macronutrient distribution of 40% in Carbohydrates, 20% Protein and 40% of Lipids in three times of food (TC3) during a 12-week period in which the following variables will be measured (Weight, Glycemic Variability: Monitor, HbA1c, Glycemia, Lipid Profile, Oxidative, FGF-21, Blood Pressure and Hunger-Satiety levels. )

During the first visit, the clinical evaluation will be developed, which consists of a complete physical examination in which vital signs, neck and head examination, chest and abdomen examination, upper and lower limb examination will be measured. As well as a complete nutritional assessment that includes, anthropometric assessment by segments using dry label tape measure, dry brand ptyometrometer and dry brand anthropometry; Body composition assessment using impedance OMRON model 512, 72hrs food consumption reminder to collect information on the feeding of each patient. Based on the information collected, the individualized TC3 plan will be prescribed and a 24/7 reminder format will be delivered to be filled out by the patient for a week, in addition to giving the indication to perform a blood glucose measurement at home once a day. in random scheme.

To assess the adherence to the nutritional plan, the patient will be summoned 15 days later to perform daily consumption assessment using the 24/7 reminder format filled out by the patient and a 72hrs reminder made through an interview. Also, Hunger-Satiety levels will be measured with the Joslin institute tables validated for the Mexican population.

If the patient adheres to the diet, blood samples will be taken to measure the variables (HbA1C, Glucose, Lipid Profile, Insulin, FGF-21) and after that place the continuous glucose monitor Medtronic model Ipro2 with in order to monitor the patient's blood glucose for 7 days.

At the end of 7 days, the patient will be summoned to remove the sensor and re-evaluate the diet.

The TC3 plan will be continued for 6 weeks, and at the end of this period the patient will be summoned again to perform blood samples to measure the variables (HbA1C, Glucose, Lipid Profile, Insulin, FGF-21), Weight, Blood pressure and hunger-satiety levels.

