#### **38. Selection criteria**

- a) Inclusion criteria (It must include the definition of the age groups, sex and the severity of the condition that will be allowed in the study)
  - a) Individuals with type 2 diabetes
  - b) Less than 10 years of evolution

c) Age between 40 and 70 years
 
d) Both genders.
 
e) With oral treatment scheme (oral hypoglycemic agents).
 
f) With HbA1c <9%
 
g) With BMI <math>\geq 25</math> to <math><40</math> kg / m^2

b) Exclusion criteria

a) Individuals with another type of diabetes.
 
b) Use of insulin.
 
c) Evolution time of more than 10 years.
 
d) Hospitalization in the last 3 months
 
e) Disease with poor short-term prognosis (for example: cancer)
 
f) Acute infection or febrile syndrome
 
g) Chronic disease other than those to be evaluated, for example: HIV, rheumatic diseases, liver cirrosis
 
h) Pregnancy
 
i) Who do not wish to participate in the study

c) Elimination criteria

a) Men or women who do not wish to continue in the study
 
b) Individuals who do not tolerate the placement of the MCGI
 
c) Individuals who are not attached to the meal plan.
 
d) Individuals who do not respect the corresponding meal times during the study.

39. Outcome and variables

a) Main variables / outcomes to be measured
 
BMI (kg / m^2)
 
a) Weight
 
Glycemic variability, defined with the following indices:
 
a) MAGE (mean amplitude of glycemic excursions)
 
b) MODD (mean of daily differences)
 
c) CONGA-n
 
b) Secondary outcomes to be measured:
 
a) Fasting glucose
 
b) Triglycerides
 
c) Total Cholesterol
 
d) HbA1c
 
e) Oxidative stress
 
f) FGF21
 
g) Systolic and diastolic BP
 
h) Hunger-Satiety Scale
 
a) Frequency of measurements:

Three measurements will be made in a 12-week period with a 6-week interval between each measurement, however the sensor placed in visit 2 will be left for 7 days during which glucose measurements in the interstitial fluid will be obtained every 5 minutes.

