#### **41. Statistical analysis (Description of the processing plan and presentation of the information. Include the justification of the statistical tests that will be used)**

The distribution of the variables will be evaluated with the Shapiro-Wilk test. Descriptive statistics will be used for the presentation of the variables, estimating averages and standard deviation for variables with normal and median distribution and interquartile range for variables with non-normal distribution. The prevalence and frequencies will be expressed in terms of percentage. The variables in each group will be compared by Student's T-test or U-Mann Whitney (as appropriate). Categorical variables will be compared by Fisher's exact test or Chi square analysis. A statistically significant difference with a value of  $P < 0.05$  will be considered. The statistical program SPSS version 21 will be used for data analysis.

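### Glycaemic variability is compared without adjusting for the eligibility HbA1c, and no listed outcome shows whether an arm difference merely follows mean glucose

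*Protocol*

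**What the plan says.** Glycaemic variability stands beside weight in the primary objective (section 12) and is the second hypothesis (section 11). Section 39 defines it only through three indices: "MAGE (mean amplitude of glycemic excursions"), "MODD (mean of daily differences") and CONGA-n, whose n is not given. Neither mean sensor glucose nor any index relative to the mean is listed.

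There is one recording. Section 39 says that "the sensor placed in visit 2 will be left for 7 days". Section 16 puts that visit after the diet has begun: the plan is prescribed at the first visit and "the patient will be summoned 15 days later to perform daily consumption assessment". The first blood draw that section 16 describes is at the same visit.

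Eligibility requires glycaemia to be known beforehand. Section 16 recruits patients "with an HbA1c less than 9% and who are less than 10 years old of evolution", and section 38 repeats the HbA1c limit without a lower bound. Allocation is one block of 50 with no stratification stated (section 33).

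On analysis, section 41 says: "The variables in each group will be compared by Student's T-test or U-Mann Whitney (as appropriate"). It names no covariate.

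**The concern.** Two things are at stake.

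**Precision and chance imbalance.** With at most 25 patients per arm and any HbA1c below 9% allowed, the arms can differ by chance in glycaemia. There is no baseline index to adjust for, and the available stand-in, the eligibility HbA1c, is left out of the analysis.

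**Interpretation.** The protocol expects the three-meal plan to improve HbA1c and fasting glucose (section 12, specific objectives 1 and 2; section 26). It therefore anticipates a difference in mean glucose, yet measures variability on a scale that can move with the mean. If the indices fall, a reader will want to know whether swings shrank relative to the glucose level or only in step with it. The listed outcomes do not answer that.

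**Working it through.** **The plan's own figure.** Section 42 gives 25 per group for weight (difference 2 kg, SD 2.5, alpha 0.05, power 0.8). n = 2 × 2.5² × (1.960 + 0.842)² / 2² = 24.5, rounded up to 25. It reproduces with a two-sided alpha. No figure is given for glycaemic variability. At 25 per arm the detectable difference for any outcome is (1.960 + 0.842) × √(2/25) = 0.79 SD.

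**What adjustment is worth.** A covariate with correlation r to the outcome leaves residual variance 1 − r². The protocol gives no r; 0.4 to 0.6 is assumed.

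| r | variance cut (r²) | detectable difference, 0.79 × √(1 − r²) | unadjusted n per arm with equal precision, 25/(1 − r²) |
|---|---|---|---|
| 0.4 | 16% | 0.73 SD | 29.8 |
| 0.6 | 36% | 0.63 SD | 39.1 |

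Over both arms this equals about 10 to 28 extra patients: 2 × 4.8 = 9.6 and 2 × 14.1 = 28.2.

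**Chance imbalance.** If mean glucose has a between-patient CV of 15, 20 or 25% (assumed), the 95% chance range of the arm difference is 1.96 × CV × √(2/25) = ±8.3, ±11.1 or ±13.9%. In 20,000 simulated trials per setting with no diet effect, the unadjusted t-test rejected as follows (mean-index correlations assumed):

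| correlation of mean glucose with index | all trials | imbalance about 1 SE | imbalance about 2 SE |
|---|---|---|---|
| 0.3 | 4.9% | 5.1% | 7.0% |
| 0.5 | 5.0% | 5.0% | 11.4% |
| 0.7 | 4.8% | 3.8% | 22.6% |

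Overall the level is held. Only a large imbalance raises the error, conditional on that imbalance having occurred.

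**How the indices respond to the mean.** On their usual definitions all three are built from differences between glucose values. Adding a constant to a trace cancels; multiplying the trace by c multiplies each index by c. The CV (SD/mean) does the opposite. Forty simulated 7-day traces at 5-minute spacing (CONGA lag of 4 hours assumed) gave these ratios to the unchanged trace:

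| change | MAGE | MODD | CONGA | CV |
|---|---|---|---|---|
| minus 15 mg/dL throughout | 1.000 | 1.000 | 1.000 | 1.11 |
| times 0.9 throughout | 0.900 | 0.900 | 0.900 | 1.000 |

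**Size of the proportional case.** Suppose one arm's glucose is lower by a fixed percentage and relative variability is unchanged. The chance of a significant result on an index at 25 per arm, for an assumed between-patient CV of the index of 25% or 35%, is:

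| glucose lower by | index CV 25% | index CV 35% |
|---|---|---|
| 5% | 11% | 8% |
| 10% | 31% | 18% |
| 15% | 62% | 36% |

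**The case against.** The strongest reply is that nothing here is an error. Allocation is random, so any chance difference in glycaemia is already part of the index's between-patient variance and of the test's standard error. That stands. A reader might infer from the ±8 to ±14% range that the comparison is biased or its false-positive rate inflated; the simulated 4.8 to 5.0% shows otherwise.

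A reader might also infer that any arm difference in mean glucose must pass in full into the three indices. It need not: a uniform shift leaves them unchanged, and only the proportional part carries through. Even then, lower absolute variability is a real effect on its own scale.

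Nor does the protocol promise a measure free of the mean. The Background sentence "It has been proposed that VG is a determinant of the microvascular complications of diabetes mellitus, regardless of hyperglycemia" reports a proposed association with complications. The same section defines variability by swings in glucose concentration, which these indices do measure.

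HbA1c and fasting glucose are secondary outcomes, drawn just before the sensor is placed, so something about glycaemia will be visible. This helps only in part. By section 23's own account HbA1c reflects the past three or four months, so two weeks into the diet it says little about the sensor week, and fasting glucose is a single time point.

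The last argument is that covariates belong in a statistical analysis plan, which is not at hand. But section 41 positively names an unadjusted test, and sections 16 and 39 fix the indices and the single on-diet trace. The point concerns those stated choices.

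**Conclusion.** The point holds as one of precision and interpretation, not of validity. The stated test keeps its 5% level but discards the only pre-diet glycaemic value that must exist for everyone. With an assumed correlation of 0.4 to 0.6, using it would cut residual variance by 16 to 36% and correct for chance imbalance in that value. A weaker correlation would bring less.

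Separately, to the extent that excursions scale with mean glucose, a lower mean can appear as lower variability. With a 10% proportional fall this yields a significant result in 18 to 31% of trials under the assumed index CVs. With a purely additive shift it does not arise. The documents give no ground for expecting one pattern over the other, and the listed outcomes would not show which occurred. Adjusting for eligibility HbA1c does not settle this second matter, because it cannot separate out a change in mean glucose caused by the diet.

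All correlations, CVs, the CONGA lag and the trace shape are assumptions. The 5% level presumes that the arms are compared as randomised; section 16 makes sampling and sensor placement depend on adherence ("If the patient adheres to the diet, blood samples will be taken to measure the variables"), which is a separate question.

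**What to change.** **Section 41.** Compare each index, on the log scale if skewed, by a linear model with arm and the pre-randomisation eligibility HbA1c as covariate. Record that value and its date for every patient.

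**Section 39.** Add mean sensor glucose and the coefficient of variation from the same 7-day trace as supportive measures, to be read beside the three indices.

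**What not to do.** Do not make a variability claim conditional on the CV: it rises by a factor of 1.11 under the additive fall above although the excursions are unchanged. Do not adjust for on-diet mean glucose, which is measured after randomisation and may itself be changed by the diet.

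**Cost.** Slightly more analysis work, one recorded value and date per patient, and two summaries from a trace already collected. Section 45 sends changes to the statistical plan to the ethics and research committees as amendments. The main weakness is that the protocol sets no assay or time window for the eligibility HbA1c. It may be a chart value of varying date, which would lower its correlation with the indices and so the gain.

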## **13. Methodology: General design.**

### a) Study design:

It is a simple blind randomized clinical trial (Information Analyst) in which a group of patients with DM2 and overweight or obesity will be subjected to a 3-course low-calorie diet (TC3), and another to a conventional hypocaloric regimen of 6 meal times (TC6) over a period of 14 weeks with the objective of evaluating the benefits, differences and impact on the health of patients, comparing weight loss, glycemic variability, HbA1c, glycemia, lipid profile , oxidative stress, FGF-21, Blood pressure and Hunger-Satiety level.

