During the first visit, the clinical evaluation will be developed, which consists of a complete physical examination in which vital signs, neck and head examination, chest and abdomen examination, upper and lower limb examination will be measured. As well as a complete nutritional assessment that includes, anthropometric assessment by segments using dry label tape measure, dry brand pellotrometer and dry brand anthropometry; Body composition assessment using impedance OMRON model 512, 72hrs food consumption reminder to collect information on the feeding of each patient. Based on the information collected, the individualized TC6 plan will be prescribed and a 24/7 reminder format will be delivered to be filled out by the patient for a week, in addition to giving the indication to perform a blood glucose measurement at home once a day. in random scheme.			
To assess the adherence to the nutritional plan, the patient will be summoned 15 days later to perform daily			

consumption assessment using the 24/7 reminder format filled out by the patient and a 72hrs reminder made through an interview. Also, Hunger-Satiety levels will be measured with the Joslin institute tables validated for the Mexican population

If the patient adheres to the diet, blood samples will be taken to measure the variables (HbA1C, Glucose, Lipid Profile, Insulin, FGF-21) and after that place the continuous glucose monitor Medtronic model Ipro2 with in order to monitor the patient's blood glucose for 7 days.

At the end of 7 days, the patient will be summoned to remove the sensor and re-evaluate the diet.

The TC6 plan will be continued for 6 weeks, and at the end of this period the patient will be summoned again to perform blood samples to measure the variables (HbA1C, Glucose, Lipid Profile, Insulin, FGF-21), Weight, Blood pressure and hunger-satiety levels.

The TC6 regime will continue for another 6 weeks. At the end of the period, the patient will be cited to re-perform blood samples to measure the variables (HbA1C, Glucose, Lipid Profile, Insulin, FGF-21), Weight, Blood Pressure and Hunger-Satiety levels

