The TC3 regime will continue for another 6 weeks. At the end of the period, the patient will be cited to re-perform blood samples to measure the variables (HbA1C, Glucose, Lipid Profile, Insulin, FGF-21), Weight, Blood Pressure and Hunger-Satiety levels.

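### Glycaemic variability, a main outcome, is recorded once, at about week 3, and only in patients judged adherent after allocation, so the arms are not compared as randomised

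*Protocol*

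**What the plan says.** Section 39 lists MAGE, MODD and CONGA-n among the main variables, and section 12 puts glycaemic variability in the primary objective. Section 39 plans three measurements six weeks apart and then adds: "however the sensor placed in visit 2 will be left for 7 days".

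Section 16, and the matching summary before section 8, give the sequence for both arms. The individualised three-meal (TC3) or six-meal (TC6) plan is prescribed at the first visit. Then "the patient will be summoned 15 days later to perform daily" consumption assessment, with adherence judged "using the 24/7 reminder format filled out by the patient and a 72hrs reminder made through an interview". The next step is conditional: "If the patient adheres to the diet, blood samples will be taken to measure the variables", and the sensor is placed after that. "At the end of 7 days, the patient will be summoned to remove the sensor and re-evaluate the diet". The later visits are described in the same way for both arms, for example "The TC3 plan will be continued for 6 weeks, and at the end of this period the patient will be summoned again" and "The TC3 regime will continue for another 6 weeks". They list blood tests, weight, blood pressure and hunger-satiety, but no sensor. Section 18 allows five visits.

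On blinding, section 13 says: "It is a simple blind randomized clinical trial (Information Analyst". Nobody else is named as blind.

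Section 38c eliminates patients who do not tolerate the monitor (b), do not keep to the meal plan (c) or do not respect the meal times (d). Section 35 gives a reason for withdrawal that concerns meal times. Section 36 says that a withdrawn patient's data are removed and that the patient receives a conventional food plan.

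**The concern.** Randomisation makes the two arms comparable as allocated. A single comparison on treatment, without a pre-diet value, is valid on that footing. It is no longer protected once the patients compared have been selected by something that happened after allocation. Here the selecting variable is adherence to the meal pattern, which is exactly what differs between the arms. If one pattern is harder to keep, the patients who pass in that arm are more strongly selected than those in the other.

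The protocol gives no threshold for adherence, relies on the patient's record and an interview, and does not say that the assessor is unaware of the arm. Nor does it say what happens to a patient who fails the assessment. Such a patient has no sensor record, and no later analysis can restore it. This is a flaw in data collection, so an analysis plan that is not at hand could not repair it.

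**Working it through.** **Plan's own figure.** Sections 27 and 42 use n = 2S²(Zα + Zβ)²/Δ², with S = 2.5 kg, Δ = 2 kg, alpha 0.05 and power 0.80. Two-sided: 2 × 6.25 × (1.960 + 0.842)² / 4 = 24.53, rounded up to 25 per group. The figure reproduces. It concerns weight only and is used below just for the arm size.

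**When variability is recorded.** The plan starts at visit 1 (day 0). Visit 2 is day 15. Sensor removal is 15 + 7 = day 22. The five visits are then start, day 15, day 22, the six-week visit and the final visit. A second sensor would need a further visit for removal, and none is left. So there is one recording, in week 3 of the allocated diet.

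**Calendar.** Three draws six weeks apart, the first at visit 2, fall on day 15, 15 + 42 = 57 and 57 + 42 = 99. Day 99 is 99/7 = 14.1 weeks after the start, and 99 − 15 = 84 days is 12 weeks. This fits the spacing in section 39 and the 14 weeks in section 13. It does not fit the 12 weeks that sections 16 and 18 attach to the diet and to total follow-up. Counting the six weeks from sensor removal gives 22 + 42 = day 64, which is 64 − 15 = 49 days after the first draw and not 42.

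**Where selection enters.** The time of randomisation is not stated, but the arm-specific plan is prescribed at visit 1, so the day-15 judgement follows allocation.

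| Step | Section | Outcomes affected |
|---|---|---|
| Adherence condition at visit 2 | 16 and summary | Variability; first draw for HbA1c, glucose, lipids, insulin, FGF21 |
| Elimination (c) and (d) | 38c | All, including weight |
| Data removal on withdrawal | 36 | All, including weight |

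**Possible size (assumed model).** The documents give no adherence rate and no correlation. Assume that adherence propensity and the variability index, in SD units, are bivariate normal with correlation −r, that a share p of an arm passes, and that there is no true effect. The mean index among those who pass is shifted by −r·L(p), with L(p) = φ(z_p)/p and z_p the normal quantile of p.

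- L(0.9) = 0.195, L(0.8) = 0.350, L(0.6) = 0.644.
- Equal passing rates: the difference is 0.
- 80% v 90%: 0.155 × 0.3 = 0.046 SD; 0.155 × 0.5 = 0.077 SD.
- 60% v 90%: 0.449 × 0.3 = 0.135 SD; 0.449 × 0.5 = 0.224 SD.

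For 60% v 90% of 25, the numbers analysed are 15 and 22.5, and the standard error is √(1/15 + 1/22.5) = 0.333 SD. The two-sided type I error by the normal approximation is 6.9% (r = 0.3) and 10.3% (r = 0.5). A simulated t-test gave 6.5% and 9.9%. At 80% v 90% the approximation gives 5.3% to 5.7%.

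**The case against.** The strongest reply is that the bias is hypothetical. Nothing in the protocol shows that the two patterns differ in adherence, and the model gives no shift at equal rates and little at 80% v 90%. That stands. A reader might infer that the comparison is tilted towards the plan that is followed less. The model yields that direction only because adherence was assumed to go with lower variability, and the documents do not establish the sign.

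A reader might also infer that the adherence condition costs power and that removing it restores power. The documents do not support this either. They give no effect size for the variability indices. If the weight ratio of 2/2.5 = 0.8 SD is borrowed, 80% adhere and non-adherent patients show no effect, measuring everyone gives 0.8 × 0.8 = 0.64 SD at 25 per arm, with power of about 60%. With the condition it is 0.8 SD at 20 per arm, with power of about 69%. The case rests on validity, not power.

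It can also be said that the time point is not hidden, since section 39 names the visit 2 sensor and section 16 dates that visit. This is right, so the missing week in sections 11, 12 and 26 is a matter of wording. The three measurements in section 39 could loosely be read to include the sensor, but the rest of that sentence, the visit contents and the visit count all point to one placement. Long periods without monitoring could be counted on an 84-day or a 106-day diet, but neither calendar fits three draws six weeks apart.

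Finally, the meal-time reason in section 35 reads as a garbled translation and may be narrower than any missed meal time. Elimination criteria (c) and (d) carry the point without it.

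**Conclusion.** The concern holds for the selection. If the protocol is followed as written, a main outcome exists only for patients who passed an adherence judgement made after allocation, without a stated threshold or stated blinding of the assessor. The elimination and data-removal rules extend the selection to all outcomes. This rests on the text alone, and confidence in that reading is high.

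The consequence is uncertain. Size and direction cannot be derived from the documents. Under the assumed model the false difference runs from 0 at equal passing rates to 0.22 SD at 60% v 90%, where the type I error reaches about 7% to 10% instead of 5%. The lack of a pre-diet recording does not invalidate a between-arm comparison; it only means that the result cannot be described as a change within patients. The 12-week and 14-week statements are a separate, lesser inconsistency.

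**What to change.** 1. In section 16 and the matching summary text, remove the adherence condition. At visit 2, draw blood and place the sensor in every randomised patient who attends and accepts it. Record adherence as data.
2. State that elimination criteria 38c (c) and (d) and the meal-time reason in section 35 end neither measurement nor use of data. State that data already collected from patients who fall under 38c (b) are kept, and that the removal in section 36 applies only to patients who ask for it. Check this against the consent wording. Analyse patients as randomised and report by arm how many lack a sensor record.
3. As a wording change in sections 11, 12 and 26, define the variability result as the between-arm difference over the visit 2 recording, at about week 3. It is neither an end-of-diet effect nor a change from a pre-diet value.
4. Reconcile the 12 weeks (sections 13f, 16 and 18) and the 14 weeks (section 13a) with the visit intervals. Draws on days 15, 57 and 99 fit the six-week spacing and the 14 weeks.

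The cost is a protocol amendment, possibly with a consent change. No visit, draw or sensor is added beyond one sensor per planned patient. Non-adherent patients, and withdrawn patients given a conventional plan, may dilute an effect that needs adherence, so power for a given effect among adherers may fall. That is the price of an as-randomised comparison. Patients who cannot tolerate the sensor will still lack a record.
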